	
Analysis of the key secondary endpoint:
 
The secondary analysis will use a similar model as primary analysis applied to the change from baseline to Week 4 in SAQ PL. The final model will provide adjusted least-squares means (LS means) estimates of the change from baseline to Week 4 in both treatment groups and their corresponding 95% confidence intervals. The difference of these estimates will be tested at the 10% 1-sided alpha level and the 95% confidence interval of the difference will be provided.
 
A safety review with a DMC meeting will start as soon as the first 19 patients will have been randomized and have finished the first week of treatment. Additional analyses for safety may be performed in this study.
 
Safety analysis:
 
Safety analyses will be descriptive, based on the safety population with a focus on BP, creatinine and cystatin C.
 
The safety analysis will focus on the TEAE period. This period is defined as the time from the first administration of the IMP to the last administration of the IMP +5 times the half-life. The half-life being from 20 to 31 hours depending on the age of the patients, a conservative estimate of 31 hours is used for all patients (thus 5 times the half-life corresponds to 5 times 31 hours ie, approximately 7 days).
 
Pharmacokinetic analysis:
 
Descriptive statistics will be provided by SAR407899 dose and time-point for observed concentrations.
 
Pharmacokinetic/pharmacodynamic analysis:
 
Scatter plots of concentrations versus primary/secondary endpoints will be provided. If relevant, some models will be provided to fit the relationship between concentrations and endpoint(s).

DURATION OF STUDY PERIOD (per patient)
	
 • Screening: up to 4 weeks before the first dosing (Day -28 to Day -1) and up to 6 weeks in patients diagnosed with MVA and stable angina without previous PCI who did not have a coronary artery angiography or CCTA in the previous 24 months but between 24 months and 5 years prior to screening and requiring CCTA in this screening period. • Titration phase: 3 weeks. • Maintenance phase: 1 week. • Total duration of treatment: 4 weeks (including titration). • Follow-up: 1 week. • Total study duration: 9 weeks (+/- 2 days) and up to 11 weeks (+/- 2 days) in patients requiring CCTA in screening period.

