- Within the first 2 weeks of study treatment patients are to be assessed as soon as possible after study drug stop, using the procedures (except PET scan) planned for the D29/end of treatment visit, including a pharmacokinetic sample (to be collected no later than 3 days after the last study drug intake).
- With at least 2 weeks of study treatment patients are to be assessed as soon as possible after study drug stop, using the procedures planned for the D29/end of treatment visit, including a pharmacokinetic sample (to be collected no later than 3 days after the last study drug intake). PET scan can be performed up to 3 days after study drug discontinuation.

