10.1.5 Visit 6: End of study: Day 36 (+/- 2 days)

Visit at clinical site:

- Patient's diary review.
- Vital signs (BP & heart rate measurements including search of hypotension) and resting 12 lead ECG.
- Blood sampling for hematology, biochemistry.
- Blood sampling for renal function (blood creatinine and cystatin C).
- AEs collection.
- Collection of information about any concomitant medications.

Study restriction(s)

There is no restriction of meals with regard to contents or time schedule.

This visit is not mandatory in case of premature treatment discontinuation.

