10.3.4 Procedure and consequence for patient withdrawal from study

The patients may withdraw from the study before study completion if they decide to do so, at any time and irrespective of the reason. Withdrawal of consent for treatment should be distinguished from withdrawal of consent for follow-up visits and from withdrawal of consent for non-patient contact follow-up, eg, medical records check. Patients requesting withdrawal should be informed that withdrawal of consent for follow-up may jeopardize the public health value of the study.

Every effort should be made to convince the patients to perform the end of study treatment/D29 with assessment of primary and secondary endpoints including blood samples and pharmacokinetic samples. The end of study visit (D36) one week later should be done. This visit is not mandatory in case of premature study drug discontinuation.

Patients who withdraw should be explicitly asked about the contribution of possible AEs to their decision to withdraw consent, and any AE information elicited should be documented. Preferably the patient should withdraw consent in writing and, if the patient or the patient's representative refuses or is physically unavailable, the site should document and sign the reason for the patient's failure to withdraw consent in writing.

All study withdrawals should be recorded by the Investigator in the appropriate screens of the e-CRF and in the patient's medical records when considered as confirmed. In the medical record, at least the date of the withdrawal and the reason should be documented.

For patients who fail to return to the site, unless the patient withdraws consent for follow-up, the investigator should make the best effort to re-contact the patient (eg, contact patient's family or private physician, review available registries or health care databases), and to determine his/her health status, including at least his/her vital status. Attempts to contact such patients must be documented in the patient's records (eg, times and dates of attempted telephone contact, receipt for sending a registered letter). The statistical analysis plan will specify how these patients inevaluable for their primary endpoints will be considered.

Patients who have withdrawn from the study cannot be re-randomized (treated) in the study. Their inclusion and treatment numbers must not be reused.

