10.4.3 General guidelines for reporting adverse events

- All AEs, regardless of seriousness or relationship to IMP/NIMP, spanning from the signature of the informed consent form until the end of the study as defined by the protocol for that patient, are to be recorded on the corresponding page(s) or screen(s) of the eCRF:
 - Whenever possible, diagnosis or single syndrome should be reported instead of symptoms. The Investigator should specify the date of onset, intensity, action taken with respect to IMP, corrective treatment/therapy given, additional investigations performed, outcome, and his/her opinion as to whether there is a reasonable possibility that the AE was caused by the IMP/NIMP or by the study procedure(s),
 - The Investigator should take appropriate measures to follow all AEs until clinical recovery is complete and laboratory results have returned to normal, or until progression has been stabilized, or until death, in order to ensure the safety of the patients. This may imply that observations will continue beyond the last planned visit per protocol, and that additional investigations may be requested by the monitoring team up to as noticed by the Sponsor. Patients who experience an ongoing SAE or an AESI, at the prespecified study end-date, should be followed until resolution, stabilization, or death and related data will be collected,
 - When treatment is prematurely discontinued, the patient's observations will continue until the end of the study as defined by the protocol for that patient,
 - Laboratory, vital signs or ECG abnormalities are to be recorded as AEs only if:
 - Symptomatic and/or,
 - Requiring either corrective treatment or consultation, and/or,
 - Leading to IMP discontinuation or modification of dosing, and/or,
 - Fulfilling a seriousness criterion, and/or,
 - Defined as an AESI.

Instructions for AE reporting are summarized in [Table 5](#).

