11.4.3 Analyses of safety data

The summary of safety results will be presented by treatment group on the basis of the safety population.

All safety analyses will be performed on the safety population using the following common rules:

- The baseline value is defined generally as the last available value before randomization.
- The analysis of the safety variables will be essentially descriptive and no hypothesis testing is planned.

The following definitions will be applied to laboratory parameters, vital signs and ECG.

- The potentially clinically significant abnormality (PCSA) values are defined as abnormal values considered medically important by the Sponsor according to predefined criteria/thresholds based on literature review and defined by the Sponsor for clinical laboratory tests, vital signs, and ECG.

PCSA criteria will determine which patients had at least 1 PCSA during the TEAE period, taking into account all evaluations performed during the TEAE period, including unscheduled or repeated evaluations. The number of all such patients will be the numerator for the PCSA percentage.

Observation period

- The TEAE observation period is defined as the time from the first dose of IMP up to 7 days after the last dose of IMP.
- The on-study period is defined as the time from randomization until the end of the study (see definition in [Section 6.2.1](#)).

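### The end-of-study visit is optional after an early stop, so 4 to 7 of the 7 post-dose days in the adverse-event window have no required contact

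*Protocol*

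**What the plan says.** **How long events count.** Protocol 11.4.3 defines the treatment-emergent adverse event (TEAE) period as the "time from the first dose of IMP up to 7 days after the last dose of IMP". The Clinical Trial Summary gives the basis: "5 times the half-life corresponds to 5 times 31 hours ie, approximately 7 days". Potentially clinically significant abnormalities (PCSAs) in laboratory values, vital signs and ECG are counted from evaluations made inside that same period. Section 11.4.3.1 sets the safety population as the denominator for TEAE percentages. No denominator is stated for PCSA percentages.

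**What observation is expected.** Section 4.4 says patients are followed for a week after treatment ends so that washout events are collected. Section 9.2.1 collects spontaneously reported events to the end of study at Day 36. Section 10.4.3 says that after an early stop the patient's "observations will continue until the end of the study as defined by the protocol for that patient".

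**What is required after an early stop.** Section 10.1.4 says "patients are to be assessed as soon as possible after study drug stop". The Day 29 procedures apply, with a PK sample no later than 3 days after the last intake and no PET scan if the stop falls within the first 2 weeks. Section 10.3.4 then says "The end of study visit (D36) one week later should be done", followed at once by "This visit is not mandatory in case of premature study drug discontinuation". Section 10.1.5, headed Day 36 (+/- 2 days), says the same: "This visit is not mandatory in case of premature treatment discontinuation".

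**SAP.** Section 1.2 reports 10 randomized patients and a descriptive analysis. Table 1 keeps the adverse-event incidence tables and the PCSA incidence.

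**The concern.** The counting rule runs to last dose + 7 days for everyone. The visit that serves the washout week is optional for patients who stop early. Their one required visit comes near the start of that week, and no section names a later contact at which a new event would be reported or a measurement taken.

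A patient who is not contacted adds no event but stays in the TEAE denominator. An abnormality that nobody measured cannot be counted. Ascertainment can then differ between completers and early stoppers, and between arms if stopping rates differ. A difference is plausible. Stopping is partly driven by adverse events (10.3.2) and by a creatinine rule (8.1.1), and orthostatic hypotension was dose-related in earlier studies (4.2). Any shortfall would then fall mainly on the active arm, in a trial whose safety objective centres on hypotension.

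**Working it through.** **1. The plan's own figure.** 5 × 31 h = 155 h, and 155/24 = 6.46 days, stated as approximately 7 days. It reproduces. With the shorter half-life of 20 h, 5 × 20 = 100 h = 4.17 days.

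**2. Days without required contact after an early stop.** Let d be the days from last dose to the required visit. The only dated limit near that visit is 3 days, for the PK sample, so d is taken as 0 to 3. Uncovered days = 7 − d.

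| d | Uncovered days | Share of the 7 days |
|---|---|---|
| 0 | 7 | 100% |
| 1 | 6 | 86% |
| 2 | 5 | 71% |
| 3 | 4 | 57% |

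As an example, a last dose on Day 8 gives a TEAE period of 8 + 7 = 15 days. If the visit is the next day, 6/15 = 40% has no required contact. If it is at d = 3, the share is 4/15 = 27%.

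**3. Washout is not over at that visit.** Assuming simple exponential decline, the fraction left at d = 3 is 2^(−72/31) = 20% with a 31 h half-life and 2^(−72/20) = 8% with 20 h.

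**4. Completers.** The last dose falls on Day 29, or up to Day 31 if the PET scan is delayed (1.3.1 and 1.3.2, footnotes d and i). Visit 6 is on Day 34 to 38.

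- Last dose Day 29: the window closes on Day 36. A visit on Day 34 leaves 2 days uncovered.
- Last dose Day 31: the window closes on Day 38. A visit on Day 36 leaves 2 days and one on Day 34 leaves 4.

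On nominal timing (Day 29, then Day 36) nothing is uncovered.

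**5. Would a compulsory Day 36 visit help?** For a last dose on Day 8, 15 or 22 the window closes on Day 15, 22 or 29. Day 36 is then 28, 21 or 14 days after the last dose, so measurements at that visit fall outside the TEAE period. Only the one-week-later wording in 10.3.4 comes near the end of the window.

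**6. Size in one arm.** The documents give no early-stopping rate, so the rate p is assumed. With 39 patients per arm (11.1), k = 39p stoppers, stop day s from 7 to 21, and completers treated for 29 days and counted as fully covered:

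share uncovered = k(7 − d) / [(39 − k)(29 + 7) + k(s + 7)]

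For p = 10% and s = 7, k = 3.9 and the denominator is 35.1 × 36 + 3.9 × 14 = 1,318.2 person-days. At d = 3, 15.6/1,318.2 = 1.18%. At d = 0, 27.3/1,318.2 = 2.07%.

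| Assumed p | Share at d = 3 | Share at d = 0 |
|---|---|---|
| 5% | 0.56–0.57% | 0.98–1.00% |
| 10% | 1.14–1.18% | 1.99–2.07% |
| 20% | 2.33–2.53% | 4.07–4.43% |
| 30% | 3.57–4.08% | 6.25–7.14% |

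The ranges run over the stop days. These are shares of time without required contact, not shares of events missed.

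**The case against.** The strongest reply is that an optional visit does not end event collection. Sections 4.4, 9.2.1 and 10.4.3 keep collection open after an early stop, and section 10.3 asks that the patient stay in the study as long as possible. The event that caused the stop is seen at the discontinuation visit and followed until it resolves or stabilizes (10.3.3, 10.4.3). That visit also measures creatinine and cystatin C. Section 4.2 places symptomatic orthostatic hypotension mainly after the first dose, not after stopping. Completers are not always covered either. With 10 patients and descriptive tables, little depends on the point.

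Much of this stands, and it limits the concern to new or late events and to abnormalities nobody measured. It does not remove it. Section 9.2.1 relies on spontaneous reports, and no section requires a contact at which an early stopper would make one. Following known events does not find new ones. Section 10.4.3 refers to that patient's own end of study, which is unclear once the last visit is optional. SAP section 1.3 counts doubtful events as treatment-emergent but cannot restore events never collected. The SAP's TEAE listing and its laboratory PCSA listing show patients with findings, so they do not reveal who went unobserved.

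**Conclusion.** The sections conflict and should be reconciled. After an early stop, 4 to 7 of the 7 post-dose days have no required contact, taking the discontinuation visit to fall within 3 days. New or late events and abnormalities may be missed. If stopping is more frequent on active drug, TEAE and PCSA incidence in that arm may be understated. At an assumed 10% stopping rate the gap is about 1% to 2% of an arm's TEAE person-days. Across assumed rates of 5% to 30% it is about 0.6% to 7%.

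A reader might infer four stronger things that the documents do not support:

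- That events are in fact under-ascertained, or incidence biased. Collection formally stays open, so this is a risk.
- That early stoppers are the patients most likely to have late events. No figure in the documents shows this; that stopping is partly event-driven is only indirect support.
- That completers are fully covered. The visit windows can leave them 2 to 4 uncovered days.
- That renal measurements after stopping are lost. Creatinine and cystatin C are taken at the discontinuation visit; only later values may be absent.

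The point is worth correcting, though its practical weight in a trial that ended with 10 randomized patients is small.

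**What to change.** Reconcile Protocol sections 4.4, 9.2.1, 10.1.5, 10.3.4 and 10.4.3 so that adverse-event collection is tied to each patient's own last dose + 7 days and not to calendar Day 36. A telephone contact on or just after that day would serve. The same rule would close the gap for completers with a delayed last dose or an early Visit 6.

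A call yields no blood pressure, ECG or laboratory values, so it cannot complete the PCSA counts. The SAP should therefore also flag treated patients whose TEAE window was not fully observed. The individual treatment-intake listing in SAP Table 1 could carry the flag, with a footnote giving the number flagged per arm in the TEAE and PCSA incidence tables. No extra set of tables is needed at this sample size.

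The cost is a wording change in the sections named, one contact for a few patients, and one derived flag. The flag remains feasible for the terminated trial if last-dose and last-contact dates are in the database.

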10.2 DEFINITION OF SOURCE DATA

All evaluations listed below that are reported in the CRF must be supported by appropriately signed identified source documentation related to:

- Patient identification.
- Medical/surgical history.
- Dates and times of visits and assessments.
- Physical examination, cardiological examination.
- Vital signs, body weight and height, body temperature.
- Resting 12-lead ECGs results.
- Laboratory result.
- Pharmacokinetic & Biomarker time points.

- Adverse events.
- IMP administration.
- Previous/concomitant medication, including start of medication and time of change in dosing regimen.
- SAQ.
- PET scan CFR reports of assessments performed during the patient's study participation.
- CCTA results if any.
- Coronary artery angiography results if any.
- Patient's diaries.
- Patient perceptions of treatment and symptoms.
- Resources utilization.

10.3 HANDLING OF PATIENT TEMPORARY OR PERMANENT TREATMENT DISCONTINUATION AND OF PATIENT STUDY DISCONTINUATION

The IMP should be continued whenever possible. Permanent IMP discontinuation should be a last resort. Any IMP discontinuation should be fully documented in the CRF. In any case, the patient should remain in the study as long as possible.

- Pregnancy will lead to definitive treatment discontinuation in all cases.
- Additional stopping rules described in [Appendix A](#) and [Section 8.1](#) should be applied, if applicable.

10.3.1 Temporary treatment discontinuation with investigational medicinal product(s)

Not applicable.

10.3.2 Permanent treatment discontinuation with investigational medicinal product(s)

Permanent treatment discontinuation is any treatment discontinuation associated with the definitive decision from the Investigator or the patient not to re-expose the patient to the IMP at any time. List of criteria for permanent treatment discontinuation

The patients may withdraw from treatment with the IMP if they decide to do so, at any time and irrespective of the reason, or this may be the Investigator's decision. All efforts should be made to document the reason(s) for treatment discontinuation and this should be documented in the e-CRF.

IMP may be permanently discontinued in case of the following events. The list is not intended to be exhaustive:

- Severe symptomatic orthostatic hypotension or postural dizziness (defined as requiring medical intervention or hospitalization) (see [Section 10.4.5](#)).

- Any serious or severe Grade 3 related adverse event will lead to permanent treatment discontinuation.
- Adverse events of lesser grade should be evaluated in the context of concomitant clinical and laboratory findings and, in the judgment of the Investigator, may be cause of permanent discontinuation of treatment for an individual subject.
- Symptoms of severe hypersensitivity or anaphylactic reactions.
- If [REDACTED] dose is not tolerated.
- Significant laboratory abnormalities (see [Section 10.4.6](#) and [Appendix A](#)):
 - Confirmed ALT >5 ULN or confirmed ALT >3 ULN and total bilirubin >2 ULN (unless the patient has Gilbert's disease documented by genetic testing),
 - Confirmed neutrophil count <1500/mm³ with or without signs of infection,
 - Suspected rhabdomyolysis with confirmed CPK >10 ULN,
 - Confirmed platelet count <100,000 cells/mm³ with or without spontaneous bleeding,
 - Confirmed decline in total white blood cell count of >50% compared to baseline and white blood cell count Grade 1 (<LLN -3000/mm³),
 - Confirmed decline in hemoglobin of >3 g/dL compared to baseline and hemoglobin level Grade 1 (< LLN -10g/dL) or higher of CTCAE terminology,
 - Confirmed QTc >500 ms.
- Pregnancy.
- Any adverse events, per Investigator's judgment, that may jeopardize the patient's safety.
- Any code breaking requested by the Investigator will lead to permanent treatment discontinuation.
- At the specific request of the Sponsor.

Any abnormal laboratory value or ECG parameter will be immediately rechecked for confirmation before making a decision of permanent discontinuation of the IMP for the concerned patient. All efforts should be made to reassess in a clinically relevant timeframe, the clinical significance of lab abnormalities and corrective actions before making a decision of permanent discontinuation of the IMP for the concerned patient.

10.3.3 Handling of patients after permanent treatment discontinuation

Patients will be followed-up and every effort should be done to have the end of study treatment/Day 29 visit completed or up to recovery or stabilization of any AE to be followed-up as specified in this protocol, whichever comes last.

All cases of permanent treatment discontinuation should be recorded by the Investigator in the appropriate pages of the e-CRF when considered as confirmed.

10.3.4 Procedure and consequence for patient withdrawal from study

The patients may withdraw from the study before study completion if they decide to do so, at any time and irrespective of the reason. Withdrawal of consent for treatment should be distinguished from withdrawal of consent for follow-up visits and from withdrawal of consent for non-patient contact follow-up, eg, medical records check. Patients requesting withdrawal should be informed that withdrawal of consent for follow-up may jeopardize the public health value of the study.

Every effort should be made to convince the patients to perform the end of study treatment/D29 with assessment of primary and secondary endpoints including blood samples and pharmacokinetic samples. The end of study visit (D36) one week later should be done. This visit is not mandatory in case of premature study drug discontinuation.

Patients who withdraw should be explicitly asked about the contribution of possible AEs to their decision to withdraw consent, and any AE information elicited should be documented. Preferably the patient should withdraw consent in writing and, if the patient or the patient's representative refuses or is physically unavailable, the site should document and sign the reason for the patient's failure to withdraw consent in writing.

All study withdrawals should be recorded by the Investigator in the appropriate screens of the e-CRF and in the patient's medical records when considered as confirmed. In the medical record, at least the date of the withdrawal and the reason should be documented.

For patients who fail to return to the site, unless the patient withdraws consent for follow-up, the investigator should make the best effort to re-contact the patient (eg, contact patient's family or private physician, review available registries or health care databases), and to determine his/her health status, including at least his/her vital status. Attempts to contact such patients must be documented in the patient's records (eg, times and dates of attempted telephone contact, receipt for sending a registered letter). The statistical analysis plan will specify how these patients inevaluable for their primary endpoints will be considered.

Patients who have withdrawn from the study cannot be re-randomized (treated) in the study. Their inclusion and treatment numbers must not be reused.

